6 PARTICIPANT SELECTION

6.1 Study Population

Participants living in Santa Clara County and experiencing homelessness who meet the inclusion and exclusion criteria will be eligible for participation in this study.

6.2 Inclusion Criteria

1. ≥ 18 years of age at baseline visit *and* has a child ≤ 17 years of age living in household.
2. A resident of Santa Clara County.
3. Experiencing homelessness, as defined by:
 - a. The Homeless Emergency Assistance and Rapid Transition to Housing Act (HEARTH Act) final rule on the definition of homelessness as published in the Federal Register in 2011; and/or
 - b. Living in a public or private space intended for temporary (≤ 6 month) residence, such as residing in a hotel/motel; residing in a space without a legal right to the

space and therefore being at threat of being asked to leave at any time (i.e., no lease or unleased); and/or being in a shared living situations intended to be temporary (i.e., being ‘doubled up’ due to lack of available and/or affordable housing).

4. Vulnerability-Index Service Prioritization Decision Assistance Tool (VI-SPDAT) score within the eligibility range for referral to rapid rehousing assistance programs in Santa Clara County (score of 4-8 for households), when available
5. Written informed consent (and assent when applicable) obtained from participant or participant’s legal representative and ability for participant to comply with the requirements of the study.

6.3 Exclusion Criteria

1. *Substantial to severe level of problematic substance use* as defined by the validated Drug Abuse Screening Test (DAST-10) (score of 6-8 or 9-10, respectively).
2. *Hazardous or harmful alcohol consumption, or active and severe alcohol use disorder*, as defined by the validated Alcohol Use Disorders Identification Test (AUDIT) (score of 8-14 and ≥ 15 , respectively).

7 CONCURRENT INTERVENTIONS

All participants will maintain eligibility for all other available housing, social, and economic assistance programs. Participants will not be excluded from receipt of any other housing assistance (nor any other assistance programs) should any be available to them during the study period.

8 STUDY INTERVENTIONS

8.1 Method of Assigning Participants to Treatment Groups

Up to 300 eligible participants will be randomly assigned to the guaranteed income group (intervention) or usual care (control group) using a computer-generated randomization scheme developed by the study team. Eligible participants will be referred by the community partners (DHSV and SSPC) to the study team for consent and enrollment into the study prior to randomization. Once participants are enrolled, they will undergo a baseline assessment before being randomly assigned to either the intervention or control group. Randomization will be stratified by referring community partner (DHSV vs SSPC). Group assignments will be known to our community partners at Sacred Heart Community Service, a neutral third community-based organization contracted by DHSV and SSPC to administer and provide support for the guaranteed income intervention; however, the core study team (investigators and core research staff at UCSF) will be blinded to group assignments.

8.2 Blinding

Due to the objectives of the study, the identity of intervention and control groups will not be known to investigators or core research staff (i.e., the UCSF study team). Due to the nature of the intervention, participants themselves will not be blinded to whether they are

assigned to the intervention arm. Community partners at Sacred Heart Community Service, who are administering the guaranteed income intervention, will also not be blinded to participants' group assignments. The following study procedures will be in place to ensure single-blinded administration of the study intervention:

Randomization will take place using a computer-generated randomization scheme integrated into the REDCap randomization module, after participants are consented and enrolled into the study. The REDCap randomization module allows specification of which study team members are blinded vs unblinded to group assignments. Because our community partners at Sacred Heart Community Service are administering the guaranteed income intervention, they will be unblinded to group assignments out of necessity, and will receive the information on individuals' group assignments via a UCSF data liaison working with the UCSF study team. The remainder of the core UCSF study team, including the PI and all key personnel (other than the biostatistician, the aforementioned data liaison, and a participant notification liaison) will be unaware and blinded to participant group assignments during the conduct of the study. The study blind will be broken on completion of the study and after the study database has been locked.

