The main risks of participating in our research evaluation activities are loss of privacy and confidentiality. There is also the risk of disappointment at not being selected for the guaranteed income intervention group. Our research evaluation activities involve secondary analyses of administrative program data, and prospective data collection through administration of surveys and conducting structured and semi-structured interviews. Our research study team will put into place comprehensive measures to protect the privacy of participants and confidentiality of their data, including a) conducting eligibility screening, informed consent, surveys and interviews by trained research staff in-person and/or by telephone in private settings where responses will not be overheard; b) informing and emphasizing that we will not disclose individual and/or identifiable data collected for the study to anyone outside of the immediate research study team including community partners, community service providers, and/or community members; c) ensuring that identifying information about individual participants will never be included in manuscripts or other presentations of data; d) storing all electronic research data on a secure, encrypted database on a UCSF server that is backed up nightly; e) storing all hard

copies of data in locked, secured cabinets behind locked office doors; and f) de-identifying data for analysis by coding data for a unique evaluation identification number for each participant, and storing the document linking participant identifiers to evaluation identification numbers separate from research data and destroying this document at the end of the evaluation. There will no immediate benefit to participants participating in research evaluation activities, though consent and enrollment in the research evaluation will be a prerequisite to being eligible to being randomized to receive the guaranteed income intervention. Individuals who are randomized to the guaranteed income intervention group will benefit from receiving the income payments.

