10.2 Visit/Assessment 2: 6-Month Survey Assessment (Month 6)

1. Record any Adverse Experiences
2. Concomitant interventions review
3. Record changes in household composition
4. Administer and record current housing situation and history of homelessness instruments, adapted from the Family Options Study and the California Statewide Survey on Homelessness.
5. Administer and record income and employment survey, adapted from the California Statewide Survey on Homelessness.
6. Record concomitant interventions in terms of receipt of assistance from other housing, social, and economic assistance programs.
7. Administer and record monthly expenditure amounts and categories, adapted from the Survey of Income and Participation.
8. Administer and record Financial Well-Being Scale, adapted from the Consumer Financial Protection Bureau (financial well-being).
9. Administer and record Material Hardship Survey, adapted from the Urban Institute Well-Being and Basic Needs and the Survey of Income and Program Participation (material hardship)
10. Administer and record the USDA Brief Food Security Survey (food security)
11. Administer and record healthcare utilization survey, adapted from the California Statewide Survey on Homelessness
12. Administer and record health conditions and functional status survey, adapted from the California Statewide Survey on Homelessness
13. Administer and record Short-Form 12 v2 (physical health)
14. Administer and record Kessler 6 (psychological health)
15. Administer and record the Generalized Self-Efficacy Scale (self-efficacy)
16. Administer and record the Brief Resilience Scale (resilience)
17. Administer and record the Perceived Stress Scale (perceived stress)
18. Administer and record the Confusion, Hubbub and Order Scale (household chaos)
19. Administer and record the Future Scale (aka the Adult Hope Scale) (agency)

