10.8 Visit/Assessment 8: 36-Month Assessment (Month 36)

1. Record any Adverse Experiences

2. Concomitant interventions review
3. Record household composition data (number of household members and children).
4. Administer and record current housing situation and history of homelessness instruments, adapted from the Family Options Study and the California Statewide Survey on Homelessness.
5. Administer and record income and employment survey, adapted from the California Statewide Survey on Homelessness.
6. Record concomitant interventions in terms of receipt of assistance from other housing, social, and economic assistance programs.
7. Administer and record monthly expenditure amounts and categories, adapted from the Survey of Income and Participation.
8. Administer and record Financial Well-Being Scale, adapted from the Consumer Financial Protection Bureau (financial well-being).
9. Administer and record Material Hardship Survey, adapted from the Urban Institute Well-Being and Basic Needs and the Survey of Income and Program Participation (material hardship)
10. Administer and record the USDA Brief Food Security Survey (food security)
11. Administer and record healthcare utilization survey, adapted from the California Statewide Survey on Homelessness
12. Administer and record health conditions and functional status survey, adapted from the California Statewide Survey on Homelessness
13. Administer and record Short-Form 12 v2 (physical health)
14. Administer and record Kessler 6 (psychological health)
15. Administer and record the Generalized Self-Efficacy Scale (self-efficacy)
16. Administer and record the Brief Resilience Scale (resilience)
17. Administer and record the Perceived Stress Scale (perceived stress)
18. Administer and record the Confusion, Hubbub and Order Scale (household chaos)
19. Administer and record the Future Scale (aka the Adult Hope Scale) (agency)

10.9 12-Month Qualitative Interview Assessment (between months 6-12, subset of 40 participants)

1. Record any Adverse Experiences
2. Conduct semi-structured interview on impact of homelessness and guaranteed income (if applicable) on household strain and well-being, decision-making, time scarcity and future planning

10.10 24-Month Qualitative Interview Assessment (between months 18-24, subset of 40 participants)

1. Record any Adverse Experiences

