11 ADVERSE EXPERIENCE REPORTING AND DOCUMENTATION

11.1 Adverse Events

The study team will probe, via discussion with the participant, for the occurrence of adverse events (AEs) during each participant visit and record the information in the site's

source documents. Adverse events will be recorded in the patient CRF. Adverse events will be described by duration (start and stop dates and times), severity, outcome, treatment and relation to study intervention, or if unrelated, the cause. For this study, the primary potential adverse events of concern associated with the study intervention are potential loss of existing public benefits and assistance among participants, and increased income tax burden, similar to the risks that would be incurred by the general population in daily life who might experience a similar increase in overall household income.

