14.1 Data Sets Analyzed

All participants who are enrolled, complete a baseline assessment, are randomized, and, for the intervention group, agree to receive GI payments will be included in the modified intention-to-treat analyses. The primary dataset used will be data prospectively collected by the study team via the use of survey instruments and structured interviews as outlined here. We will obtain complementary administrative data on housing status, housing assistance, housing service use, social service use, and health care service use from the Santa Clara Office of Supportive Housing (Homeless Management Information System), Santa Clara Valley Medical Center Hospital & Clinics (Santa Valley Medical Center HealthLink), Santa Clara County Public Health, County of Santa Clara Social Services Agency (including the Department of Employment and Benefit Services), and from community partners (Destination: Home SV, ¡Sí Se Puede! Collective, Sacred Heart Community Service).

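### Section 8.2 says core staff stay unaware of allocation until database lock, but the protocol's own procedures do not secure this, and interviewers may sometimes learn the arm before recording the primary outcome

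*Protocol*

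**What the plan says.** Section 8.1 states that "the core study team (investigators and core research staff at UCSF) will be blinded to group assignments". Section 8.2 repeats this for the principal investigator and all key personnel, who "will be unaware and blinded to participant group assignments during the conduct of the study". It excepts three roles (biostatistician, data liaison, participant notification liaison) and breaks the blind only after completion of the study and database lock. The mechanism described is the REDCap randomization module, which controls who can see assignments. Section 8.2 also concedes that "participants themselves will not be blinded to whether they are" in the intervention arm.

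On data collection, section 2.1 has "surveys and interviews by trained research staff in-person and/or by telephone in private settings". Section 14.1 says: "The primary dataset used will be data prospectively collected by the study team via the use of survey instruments and structured interviews". Administrative data are described there as complementary.

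On adverse events, section 11.1 has the study team ask each participant at each visit and record, among other attributes, "relation to study intervention, or if unrelated, the cause". It names loss of existing public benefits and a higher income tax burden as the events of main concern. Each follow-up list in sections 10.2 to 10.8, and the early withdrawal list in 10.11 (numbering of the body text), opens with "Record any Adverse Experiences" and reaches the housing and homelessness instruments at item 4.

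**The concern.** Blinding by restricted file access works only if staff do not learn the arm in another way. Here the people described as blinded talk to participants who know their arm, on a topic tied to receiving the cash. As listed, that topic comes before the housing questions.

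The primary endpoint is a count of days experiencing homelessness. Under section 6.2 homelessness includes stays meant to be temporary, stays without a lease and doubled-up arrangements. Classifying such stays takes some judgement, and an interviewer who knows the arm may probe or code doubtful stays differently. There is also a reporting problem: a publication that follows section 8.2 would claim that staff were unaware throughout, when the procedures do not secure that.

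**Working it through.** **Who is blinded, and who does arm-revealing work**

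| Task | Where | Reserved for an unblinded role? |
|---|---|---|
| Asking about adverse events and recording relation to the intervention | 9.1.4, 11.1 | No: the study team |
| Adverse-event endpoint: benefit loss resulting directly from the payments, possible only in a recipient | 5.2 | No |
| "Conduct semi-structured interview on impact of homelessness and guaranteed income (if applicable) on household strain and well-being" | 10.9, 10.10 (subset of 40) | No |
| Interviews on why a payment schedule was preferred | 5.2 | No |
| Investigator's opinion on discontinuing the intervention after an adverse event | 12.1 | No: the investigator, whom 8.1 lists as blinded |
| Contacting the secondary payee if the participant is incarcerated | 12.4(a) | No: the study team speaks as we, distinct from the community partners |

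The protocol text does not ask participants to withhold their arm, does not provide a separate adverse-event assessor, and does not require the housing questions to come first.

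**Order in the visit lists**

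- Months 6, 12, 18, 24, 27, 30 and 36, and early withdrawal: item 1 adverse experiences, item 2 concomitant interventions review, item 3 household composition, item 4 housing and homelessness instruments, item 5 income and employment, item 6 assistance received.
- Baseline (10.1): no adverse-experience item, and randomization is item 22, so there is no arm to reveal.
- Appendix 1 also lists adverse experiences above the current housing situation, but puts social services and assistance below it.

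The housing and homelessness instruments are the visit items that record homelessness. With section 14.1 naming survey data as the primary dataset, I take them as the source of the primary endpoint.

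**What a bias would do (illustration only)**

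Inputs from 14.6: SD 74.0, mean 52.3 days, 150 or 110 per arm, two-sided 0.05.

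The plan's own figures first. SE = 74.0 × √(2/n), which is 8.54 days at 150 per arm and 9.98 days at 110. Detectable difference = (1.960 + 0.842) × SE = 23.9 and 28.0 days, against 24.0 and 28.0 stated. Power at the stated differences is 80.2% and 80.1%. The plan's figures reproduce, and the concern does not rest on them.

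Now assume no true effect and a between-arm shift of b days in the mean count through differential recording. The rejection rate is 1 − Φ(1.960 − b/SE) + Φ(−1.960 − b/SE):

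| Assumed b (days) | b / 52.3 | 150 per arm | 110 per arm |
|---|---|---|---|
| 0 | 0% | 5.0% | 5.0% |
| 2.5 | 4.8% | 6.0% | 5.7% |
| 5 | 9.6% | 9.0% | 7.9% |
| 10 | 19.1% | 21.6% | 17.1% |

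The shifts are assumptions; nothing in the protocol estimates them. The formula compares two means, as in the sample-size section, and is not the planned Poisson regression. Because b is an average over all participants, unblinding in only some interviews would need a larger error in those interviews to produce the same b.

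**The case against.** Much of the case on the other side stands and limits the point.

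- The protocol does not say that the list numbers are the order of administration. Concomitant assistance appears twice in each follow-up list, and Appendix 1 marks adverse experiences at baseline although 10.1 has no such item, so the lists read partly as checklists. Disclosure before the housing questions is therefore a likely inference, not a stated procedure.
- A reader might infer that every interview reveals the arm. The documents do not support that. Item 1 covers any adverse experience, 11.1 provides for unrelated events, and the arm emerges only when a participant reports an event and connects it with the payments. The waivers and Hold Harmless fund in 2.1 are meant to limit benefit loss. The protocol also does not say that the interviewer is the person who judges relatedness, or that survey interviewers conduct the qualitative interviews.
- A reader might treat the assistance review at item 2 as an equal route. Section 9.1.1 limits it to other programs, and both arms keep access to those under section 7. It is at most a minor route.
- A reader might spread the 24-day detectable difference over 36 months, get 24/36 = 0.67 days per month, and conclude that a trivial recording error would match it. That does not follow. 24 days is 24/52.3 = 46% of the assumed mean, and 14.6 does not say what period that mean covers.
- Participants know their arm and report their own housing, so blinding the interviewer can remove only part of the possible bias. Structured instruments and complementary administrative data also restrict interviewer discretion to some degree.

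None of this rescues the wording of 8.2. It promises unawareness until database lock, backs it only with access control, and leaves arm-revealing tasks with staff it calls blinded. That is a conflict within the protocol, not a detail deferred to an analysis plan.

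**Conclusion.** The stated blinding property is wrong as written, and a cheap improvement is available. The procedures deliver something narrower: interviewers are not given the allocation. They do not deliver staff who remain unaware throughout.

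The item appears at all seven follow-up visits and at early withdrawal. That describes where the exposure can arise, not how often it will. No frequency of unblinding and no size of bias can be derived from the documents, and the table of assumed shifts must not be read as an estimate of either. The conclusion that the arm may be known before the primary outcome is recorded assumes that the lists are followed roughly as numbered and that the same staff ask items 1 and 4. The conflict between 8.2 and the arm-revealing tasks needs neither assumption. The point is of modest importance.

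**What to change.** 1. In 10.2 to 10.8 and 10.11, state that the housing and homelessness instrument is completed and saved before the adverse-experience, assistance and income items.
2. In 8.2, replace the claim that staff will be unaware throughout with what is delivered: interviewers are not told the allocation, and the primary outcome is recorded before items likely to reveal it. Bring the matching sentences in 8.1 and 14.6 into line.
3. Add one item directly after the housing instrument recording whether the interviewer knew the arm by then, so that the report can state how often the blind held.

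The cost is a reordered survey form, a few sentences and one extra item, with no added staff. The limits should be acknowledged: the new order protects less at later visits if the same interviewer returns, and it does nothing about self-report bias from unblinded participants.

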9 STUDY PROCEDURES AND GUIDELINES

A Schedule of Events representing the data collection procedures to be performed for the duration of the study is diagrammed in Appendix 1.

Prior to conducting any study-related activities, we will obtain written informed consent and the Health Insurance Portability and Accountability Act (HIPAA) authorization must be signed and dated by the participant or participant's legal representative. Participants will be eligible to participate in even if they decline HIPAA authorization and release of health-related data from health care providers (Santa Clara Valley Medical Hospital & Clinics). This HIPAA authorization has also been reviewed and approved by Santa Clara County Counsel for authorization of release of public benefits program-related data (i.e., social services-related data) from Santa Clara County Public Health and Santa Clara County Social Services Agency as detailed in section 14.1).

9.1 Clinical Assessments

9.1.1 Concomitant Interventions

All concomitant interventions in terms of receipt of assistance from other housing, social, and economic assistance programs will be documented at Baseline/Screening and 6-month follow-up surveys and early termination when possible. The type, frequency, and amount of assistance services will be captured. These data on concomitant interventions will be supplemented with administrative data from relevant Santa Clara County agencies and community organizations if available.

9.1.2 Demographics

Demographic information (date of birth, sex/gender, race/ethnicity, education) will be recorded at Baseline.

